11.1.2 Unsolicited Adverse Events

All spontaneous unsolicited AEs occurring up to Day 49 will be reported in the “Adverse Event” screen in the subject’s eCRF, irrespective of intensity or whether or not they are considered to be vaccination-related. Thereafter, from Day 50 to the end of the study, SAEs, AEs leading to withdrawal, MAAEs and AESIs will be monitored and reported in the eCRF.

The intensity of unsolicited AEs will be graded as: mild (1), moderate (2), severe (3) or potentially life threatening (4), according to the FDA Guidance for Industry [FDA 2007]. Their causal relationship with the study vaccine will be assessed by the Investigator (definitely not related, probably not related, possibly related, probably related or definitely related); see Section 12.1.9 for a definition of these causal relationships.

11.1.3 SARS-CoV-2 Positive Reports

Confirmed COVID-19 cases will be recorded as AEs. Also, confirmed COVID-19 cases will be reported according to the process for reporting SAEs, in the event such case may meet the definition of an SAE. Any potential COVID-19 case that is not a confirmed event and does meet the criteria for an SAE will be reported. The Investigator must report the SAE to MTPC within 24 hours (see Section 12.1.6) of becoming or being made aware.

Following the first vaccination, each subject will be asked to report symptoms associated with COVID-19 during the study. COVID-19 will be defined as the presence of a laboratory-confirmed (virologic method) SARS-CoV-2 infection with the occurrence of a new onset of one or more of the following symptoms:

- ◆ Fever or chills;
- ◆ Cough;
- ◆ Shortness of breath or difficulty breathing;
- ◆ Fatigue;
- ◆ Muscle or body aches;
- ◆ Headache;
- ◆ New loss of taste or smell;
- ◆ Sore throat;
- ◆ Congestion or runny nose;
- ◆ Nausea or vomiting;
- ◆ Diarrhea.

11.1.4 Clinical Laboratory Tests

Blood samples for biochemistry and hematology, HIV, Hepatitis B and Hepatitis C markers in serum and urine samples for urinalysis will be collected according to the Time and Events Schedule (see Table 1). Blood samples for testing for SARS-CoV-2 antibodies will be also collected according to the Time and Events Schedules (see Table 1). In addition, serum or urine samples from all females of childbearing potential for pregnancy testing will be collected. Any laboratory result outside of the testing laboratory's normal range will be classified as 'clinically significant' or 'not clinically significant' by the site Investigator, with appropriate documentation. Any laboratory test performed at Screening with a value outside the normal range may be repeated (prior to vaccination) at the discretion of the Investigator. Repeated tests will be considered the Baseline results.

The Investigator must review the laboratory reports, document this review, and record any clinically relevant changes occurring during the study in the source documents. The tests to be performed by the laboratory are presented in Table 4.

Table 4 Clinical Laboratory Tests for the Study

Biochemistry (serum):	
Sodium	Alkaline phosphatase
Potassium	Alanine transferase (ALT)
Urea	Aspartate transferase (AST)
Creatinine	Gamma glutamyltransferase (GGT)
Glucose	Cholesterol (total, HDL, LDL)
Bilirubin (total)	Triglyceride
Albumin	Chloride
Total protein	Calcium
	Phosphorus
Haematology:	
Haemoglobin	Mean cell haemoglobin (MCH)
Hematocrit	Mean cell concentration (MCHC)
Red blood cells	Mean cell volume (MCV)
Platelets	Lymphocytes
Mean platelet volume (MPV)	Monocytes
White cell count (total, WBC)	Eosinophils
Neutrophils	Basophils
Serology:	
HIV	Hepatitis B
Hepatitis C	
Urinalysis:	
Macroscopic examination (color, aspect)	Glucose
pH	Protein
Specific gravity	Blood

Other clinical laboratory tests include tests to measure SARS-CoV-2 antibodies at screening, Days 201 and 386, and SARS-CoV-2 PCR at screening for all subjects, and a serum pregnancy test at screening and a urine (dipstick or similar) pregnancy test prior to randomization on Day 0 and on Days 21, 42 and 128 for all female subjects of childbearing potential.

All protocol required safety laboratory parameters are defined in study-specific documentation.

11.1.5 Vital Signs

Vital signs measurements (resting BP, PR, RR, and oral temperature) will be performed as part of screening procedures, prior to vaccination (on Day 0 and Day 21), and after the post-vaccination 30-minute surveillance period (and repeated if deemed necessary by the Investigator). In addition, vital signs measurements will be performed at the clinic site visits on Day 3, Day 24, Day 42, Day 128, Day 201, and Day 386.

Oral temperature will be collected in degrees Celsius using a digital thermometer provided by MTPC. The OT measurement should not be collected immediately following consumption of a hot or cold beverage or after smoking.

BP will be taken after the subject has been in a seated position as per the site's standard procedure. BP should be taken by cuff (manual or automated are both acceptable). BP, PR and RR may be repeated once if judged necessary. All measurements (including any repeats) will be recorded in the source documents.

11.1.6 Physical Examinations

A history- or symptom-directed physical examination will be performed as part of screening procedures, prior to vaccination (on Day 0 and Day 21), and after the post-vaccination 30-minute surveillance period by the (sub)Investigator. In addition, history- or symptom-directed physical examinations will be performed at the clinic site visits on Day 3, Day 24, Day 42, Day 128, Day 201, and Day 386 by (sub)Investigator.

11.1.7 Pregnancy

Female subjects who become pregnant during the study will be followed for safety. The Investigator, or his/her designee, will collect pregnancy information on any subject who becomes pregnant or is pregnant while participating in this study. The Investigator will record pregnancy information on the Pregnancy Report Form (see Appendix 2) and submit it to MTPC (see Section 12.1.6) within 24 hours of learning of a subject's pregnancy post-first vaccination. The subject will be followed to determine the outcome of the pregnancy. At the end of the pregnancy, whether full-term or premature, information on the status of the mother and child will be forwarded to MTPC, if available. Generally, follow-up will be no longer than eight weeks following the estimated delivery date.

While pregnancy itself and elective termination of a pregnancy for non-medical reasons are not considered to be an AE/SAE, any pregnancy complication or elective termination of a pregnancy for medical reasons will be recorded in the Pregnancy Report Form or as an SAE and will be followed. A spontaneous abortion is always considered to be an SAE and will be reported as such. Furthermore, any SAE occurring as a result of a post-study pregnancy and considered reasonably related in time to receipt of the investigational product by the Investigator, will be reported to MTPC. While the Investigator is not obligated to actively seek this information from former study subjects, he/she may learn of a pregnancy through spontaneous reporting.

11.2 Immunogenicity Evaluations

Immunogenicity will be evaluated by the humoral immune response (serology) and the CMI response induced in subjects on Days 0, 21, 42, 128 (serology only), 201, and 386 in all subjects.

For CMI response, blood samples may not be collected for all subjects.

The blood samples for immunogenicity will be analyzed in one or more central laboratories; information on processing and the central laboratories will be provided in the study-specific documentation.

11.2.1 Immunogenicity Endpoints

See Section 2.2.1, 2.2.2 and 2.2.3.

Point estimates and 95 %CI will be calculated for all immunogenicity endpoints and responses

for the treatment groups will be compared using descriptive statistics.

12 ASSURANCE OF SUBJECT SAFETY

12.1 Definitions

12.1.1 Serious Adverse Events

An SAE is any untoward medical occurrence (whether or not considered to be related to the study vaccine) that, at any dose:

- ◆ Results in death;
- ◆ Is life-threatening (at the time of the event);

Note: the term “life-threatening” in the definition of an SAE refers to an event that put the subject at risk of death at the time of the event; it does not refer to an event that hypothetically might have caused death if it were more severe;

- ◆ Requires inpatient hospitalization (≥ 24 hours) or prolongation of existing hospitalization (elective hospitalizations/procedures for pre-existing conditions that have not worsened are excluded);
- ◆ Results in persistent or significant disability/incapacity;
- ◆ Is a congenital abnormality/birth defect;
- ◆ Is another medically important event.

Medical and scientific judgment should be exercised in deciding whether expedited reporting is appropriate in other situations, such as important medical events that may not be immediately life-threatening or result in death or hospitalization but that may jeopardize the subject’s health or may require an intervention to prevent one of the other outcomes listed in the definition above. These events should be considered serious. Examples of such events are intensive treatment in an emergency room for allergic bronchospasm, blood dyscrasias, or convulsions that do not result in hospitalization or the development of drug dependency or drug abuse. See Section 12.1.6 for initial SAE reporting by the Investigator.

12.1.2 Adverse Events

An AE or adverse experience is defined as any untoward medical occurrence in a subject or clinical investigation subject who was administered a pharmaceutical product, with or without a causal relationship with the treatment. An AE can be any unfavorable and unintended sign, symptom, or disease temporally associated with the use of a medicinal product, whether or not related to a medicinal product.

Information such as the date and time of onset and resolution (duration), intensity (defined below), seriousness, any required treatment or action taken, outcome, relationship to the investigational vaccine, and whether the AE caused withdrawal from the study will be collected.

The intensity of all AEs will be graded as mild (1), moderate (2) severe (3), or potentially life threatening (4), according to the FDA Guidance for Industry: Toxicity Grading Scale for Healthy Adult and Adolescent Volunteers Enrolled in Preventive Vaccine Clinical Trials [FDA 2007] for the events covered in the guidance and the following definitions for all other events:

Mild (Grade 1):	The AE is easily tolerated and does not interfere with usual activity;
Moderate (Grade 2):	The AE interferes with daily activity, but the subject is still able to function;
Severe (Grade 3):	The AE is incapacitating and the subject is unable to work or complete usual activity;
Potentially life-threatening (Grade 4):	The AE is likely to be life-threatening if not treated in a timely manner.

Note: According to the FDA Guidance for Industry: Toxicity Grading Scale for Healthy Adult and Adolescent Volunteers Enrolled in Preventive Vaccine Clinical Trials [FDA 2007]: *“Nonetheless, we believe that categorization or grading of data as outlined in this document is supplementary to and should not replace full and complete data analysis. These guidelines for toxicity grading scales are primarily intended for healthy adult and adolescent volunteers.”* and *“Toxicity grading scales for laboratory abnormalities should consider the local laboratory reference values when the parameter limit values are defined. The characterization of laboratory parameters among some populations of healthy adults and adolescents may require the exercise of clinical judgment, for example, consideration of the potential for ethnic differences in white blood cell (WBC) counts or gender differences in creatine phosphokinase (CPK) values.”*

The Investigator will be instructed to closely monitor each subject who experiences an AE (whether ascribed to the investigational product or not) until the outcome of the AE has been determined.

If any of the solicited local or systemic AEs persist beyond Day 7 after each vaccination (when applicable), these will also be recorded as unsolicited AEs. In this case, the AE start will be set as eight days post-vaccination. The subject will be requested to note when the AE resolves and to report this information to the Investigator or site staff at the next visit at the clinical site or contact.

The clinical importance of AEs will be determined based upon the Investigator's judgment. The Investigator must ensure that any sample obtained to follow-up on an AE is properly labeled and stored. The Investigator and site staff should institute any supplementary investigations of significant AEs based on the clinical assessment of the likely causative factor. This may include seeking the opinion of a specialist in the field of the AE.

All unsolicited AEs occurring up to Day 49 must be reported in the "Adverse Event" screen in the subject's eCRF, irrespective of intensity or whether or not they are considered to be vaccination-related. Thereafter, from Day 50 through to Day 386, SAEs, MAAEs, AEs leading to withdrawal, and AESIs will be monitored and reported in the eCRF. Additional details on eCRF entries can be found in the eCRF completion guidelines.

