2.2 Study Endpoints

2.2.1 Primary Endpoints

The following primary immunogenicity and safety endpoints are for Groups 1 (3.75 µg of MT-2766) and Group 2 (placebo for MT-2766 3.75 µg).

Safety:

1. The incidences, severity, and investigator-assessed causality of immediate adverse events (AEs) that occur within 30 minutes of first (Day 0) and second (Day 21) injections.
2. The incidences and severity of the following solicited AEs that develop within 7 days of first (Day 0) and second (Day 21) injections: (i) local AEs (injection site erythema, injection site swelling, injection site induration, and injection site pain) and (ii) systemic AEs (fever, headache, fatigue, muscle aches, joint aches, chills, a feeling of general discomfort, swelling in the axilla, and swelling in the neck).
3. The incidences, severity, and investigator-assessed causality of unsolicited AEs that develop within 21 days of first (Day 0) and second (Day 21) injections.
4. The incidences of serious AEs (SAEs), medically attended AEs (MAAEs), AEs leading to withdrawal, AEs of special interest (AESIs), and deaths up to 21 days following first (Day 0) and second (Day 21) injections. AESIs include vaccine-associated enhanced diseases (VAED), hypersensitivity reactions, and potential immune-mediated diseases (pIMDs).

Immunogenicity:

1. SARS-CoV-2 neutralizing antibody (Nab) responses will be analyzed on Days 0, 21, and 42 using the following parameters: geometric mean antibody titer (GMT), seroconversion (SC) rate, and geometric mean fold rise (GMFR);
2. SARS-CoV-2-specific T helper 1 (Th1) cell-mediated immune (CMI) responses will be measured on Days 0, 21, and 42 using the interferon (IFN)- γ enzyme-linked immunospot (ELISpot) assay;
3. SARS-CoV-2-specific T helper 2 (Th2) CMI responses will be measured on Days 0, 21, and 42 using the interleukin (IL)-4 ELISpot assay.

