12.1.9 Causal Relationship

The Investigator must make the determination of relationship to the study vaccine for each unsolicited AE. The causal relationship of all solicited local and systemic AEs will be considered related. The Investigator should decide whether, in his/her medical judgment, there is a reasonable possibility that the event may have been caused by the investigational vaccine. If there is any valid reason, even if undetermined or untested, for suspecting a possible cause-and-effect relationship between the investigational vaccine and the occurrence of the AE, then the AE should be considered “definitely related”, “probably related”, or “possibly related”. Otherwise, if no valid reason exists for suggesting a possible relationship, then the AE should be classified as “probably not related” or “definitely not related”. The following guidance should be followed:

Definitely Not Related:	The AE is clearly not related to the administration of the study vaccine. Another cause of the event is most plausible; and/or a clinically plausible temporal sequence is inconsistent with the onset of the event and the study vaccine administration; and/or a causal relationship is considered biologically implausible.
Probably Not Related:	There is no medical evidence to suggest that the AE is related to the study vaccine. The event can be readily explained by the subject's underlying medical condition or concomitant therapy or lacks a plausible temporal relationship to the study vaccine.
Possibly Related:	A direct cause and effect relationship between the study vaccine and the AE has not been demonstrated but there is a reasonable possibility that the event was caused by the study vaccine.
Probably Related:	There probably is a direct cause and effect relationship between the AE and the study vaccine. A plausible biologic mechanism and temporal relationship exist and there is no more likely explanation.
Definitely Related:	There is a direct cause and effect relationship between the AE and the study vaccine.

AE outcomes will be classified as recovered/resolved, not recovered/not resolved, recovered/resolved with sequelae, recovering/resolving, or death.

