2.2 Study Endpoint(s)

2.2.1 Primary Endpoints

The following primary immunogenicity and safety endpoints are for Groups 1 (3.75 µg of MT-2766) and Group 2 (placebo for MT-2766 3.75 µg).

Safety:

1. The incidences, severity, and investigator-assessed causality of immediate adverse events (AEs) that occur within 30 minutes of first (Day 0) and second (Day 21) injections.
2. The incidences and severity of the following solicited AEs that develop within 7 days of first (Day 0) and second (Day 21) injections: (i) local AEs (injection site erythema, injection site swelling, injection site induration, and injection site pain) and (ii) systemic AEs (fever, headache, fatigue, muscle aches, joint aches, chills, a feeling of general discomfort, swelling in the axilla, and swelling in the neck).
3. The incidences, severity, and investigator-assessed causality of unsolicited AEs that develop within 21 days of first (Day 0) and second (Day 21) injections.
4. The incidences of serious AEs (SAEs), medically attended AEs (MAAEs), AEs leading to withdrawal, AEs of special interest (AESIs), and deaths up to 21 days following first (Day 0) and second (Day 21) injections. AESIs include vaccine-associated enhanced diseases (VAED), hypersensitivity reactions, and potential immune-mediated diseases (pIMDs).

Immunogenicity:

1. SARS-CoV-2 neutralizing antibody (Nab) responses will be analyzed on Days 0, 21, and 42 using the following parameters: geometric mean antibody titer (GMT), seroconversion (SC) rate, and geometric mean fold rise (GMFR);
2. SARS-CoV-2-specific T helper 1 (Th1) cell-mediated immune (CMI) responses will be measured on Days 0, 21, and 42 using the interferon (IFN)- γ enzyme-linked immunospot (ELISpot) assay;
3. SARS-CoV-2-specific T helper 2 (Th2) CMI responses will be measured on Days 0, 21, and 42 using the interleukin (IL)-4 ELISpot assay.

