7.1.3 Safety Assessments

7.1.3.1 Adverse Events

Immediate AEs are defined as any solicited local and systemic AEs and unsolicited AEs occurring within 30 minutes after vaccination. Multiple occurrences of the same event within a subject will be counted once in the maximum severity of symptoms category (potentially life threatening > severe > moderate > mild). Related is defined as AEs with a causality of “Definitely Related”, “Probably Related” or “Possibly Related”. Not related is defined as AEs with a causality of “Probably Not Related” or “Definitely Not Related”.

Adverse events will be coded according to the MedDRA version 24.1.

(1) Duration of Adverse Events

Duration of Adverse Events (days) = AE stop date – AE start date + 1

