8.3 Safety Assessments

All safety data will be listed.

Safety assessments will be made on the SAS.

Adverse events analyses will be presented for the following reporting period, as applicable:

- Day 0-21 period after vaccination 1: Any AEs meeting the following criteria will be allocated to the first vaccination (vaccination 1) and included in the Day 0-21 analysis for first vaccination:
 - Any AEs with:
 - onset date/time < date and time of second vaccine administration, if second vaccination is done,
 - else if vaccination 2 not performed, any AEs with onset date \leq date of vaccination 1 + 21
- Day 0-21 period after vaccination 2: Any AEs meeting the following criteria will be allocated to second vaccination (vaccination 2) and included in the Day 0-21 analysis for second vaccination:
 - Any AEs with onset date/time \geq Date/time of vaccination 2 and with onset date \leq date of vaccination 2 + 21.

- Day 0-21 period after last vaccination: Any AEs meeting the following criteria will be included in the Day 0-21 period after last vaccination:
 - Any AEs with onset date \leq date of last vaccination + 21 i.e.:
 - Any AEs with onset date \leq date of vaccination 2 + 21, if vaccination 2 is performed
 - Any AEs with onset date \leq date of vaccination 1 + 21, if vaccination 2 is not performed.

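### Solicited reactions that outlast Day 7 are re-entered as unsolicited AEs starting on Day 8, and no SAP rule identifies them, so they enter primary safety endpoint 3 as well as endpoint 2

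*Protocol*

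**What the plan says.** Two primary safety endpoints divide the AEs between them. Endpoint 2 covers "The incidences and severity of the following solicited AEs that develop within 7 days of first (Day 0) and second (Day 21) injections" (Protocol 2.2.1). Endpoint 3 is given in SAP 2.2.1 as "The incidences, severity, and investigator-assessed causality of unsolicited AEs that develop within 21 days" of each injection.

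Protocol 12.1.2 links the two. If a solicited reaction is still present after Day 7, "these will also be recorded as unsolicited AEs", and the date of the new record is fixed: "In this case, the AE start will be set as eight days post-vaccination". The word *also* makes this a second record and not a transfer.

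Three further rules act on that record:

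- **Period.** SAP 8.3 allocates AEs by onset. For dose 1, when dose 2 is given, the condition is "onset date/time < date and time of second vaccine administration". For dose 2, onset must fall between dose 2 and 21 days later. If dose 2 is not given, onset must be no later than 21 days after dose 1.
- **Duration.** SAP 7.1.3.1 defines "Duration of Adverse Events (days) = AE stop date", less the start date, plus one day.
- **Causality.** Solicited AEs are related by rule (Protocol 11.1.1 and 12.1.9). For the others, "The Investigator must make the determination of relationship to the study vaccine for each unsolicited AE".

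**The concern.** Endpoint 3 is meant to show what happens beyond the known, listed reactions. A sore arm that began on Day 1 and resolved on Day 10 did not develop after the solicited window, yet it enters endpoint 3 as an event with onset on Day 8. A reader of the unsolicited tables cannot separate it from an event that really began then.

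The effect is unlikely to be equal between arms. Protocol 1.6 reports more local and general reactogenicity with AS03-adjuvanted influenza vaccines than with their unadjuvanted counterparts, and the placebo here is buffered saline (Protocol 7.1.2). Reactions that last past Day 7 are therefore more likely under MT-2766. What is at stake is the reading of the unsolicited incidence, the event counts and the SOC/PT tables, where continued reactogenicity could pass for a separate finding.

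**Working it through.** The documents state no figure on this point, so there is none to reproduce. The check applies the plan's own rules.

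**1. Does the second record always fall in the endpoint 3 period?** Dose 2 is due on Day 21 ± 2, that is Day 19 to 23 (Table 1).

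- Dose 1, with dose 2 given: start is Day 8, and 8 < 19, so yes for every permitted dose 2 day.
- Dose 2: start is dose 2 + 8, and 8 ≤ 21, so yes.
- Dose 2 not given: 8 ≤ 21, so yes.

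Every reaction carried over is therefore counted in both endpoints.

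**2. Does a SAP rule take it out?** SAP 7.1.3.1 counts repeats of one event in a subject once, at the worst grade. It does not say that this works across the separate solicited and unsolicited summaries. SAP 8.3.1.2, 8.3.2 and 8.3.2.2 contain no flag, link or exclusion, and SAP 10 does not mention the matter.

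**3. Effect on incidence.** Let *b* be the proportion with another unsolicited AE and *c* the proportion with a carried-over reaction, both assumed, and independent. Incidence becomes 1 − (1 − b)(1 − c), a rise of c(1 − b). With no carry-over under placebo, that rise is also the rise in the arm difference.

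| c in MT-2766 | b = 0 | b = 20% | b = 30% |
|---|---|---|---|
| 3% | 3.0 points | 2.4 points | 2.1 points |
| 5% | 5.0 points | 4.0 points | 3.5 points |
| 10% | 10.0 points | 8.0 points | 7.0 points |

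For example, b = 20% and c = 5% gives 1 − 0.80 × 0.95 = 24%. The column b = 0 is the upper bound.

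**4. Effect on the table of most frequent AEs.** SAP 8.3.2.2 admits a term above 5% in either group. With the planned numbers, 5/100 = 5% does not qualify and 6/100 does; 1/25 = 4% does not and 2/25 = 8% does. The threshold applies to each preferred term, not to any prolonged reaction. If one term carried over at an assumed 2%, 5% or 10%, the binomial probability of at least 6 of 100 in Group 1 is 0.015, 0.38 or 0.94.

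**5. Effect on duration.** True length is stop − onset + 1. The unsolicited record gives stop − 8 + 1. The difference is 8 − onset day, whatever the stop date.

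| Onset day | Stop day | True length | Unsolicited record | Loss |
|---|---|---|---|---|
| 0 | 10 | 11 | 3 | 8 |
| 1 | 10 | 10 | 3 | 7 |
| 1 | 14 | 14 | 7 | 7 |
| 7 | 10 | 4 | 3 | 1 |

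**6. Causality.** The solicited record is related by rule, while the unsolicited record carries the investigator's judgement. The two records of one reaction may differ. Nothing in the documents shows how often they would.

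**The case against.** The strongest reply is that the rule is explicit and useful. The diary closes on the evening of Day 7, and the second record keeps the reaction under follow-up and captures its resolution. The plan does not contradict itself here. That stands, and it is why the entry should be kept. It does not answer the lack of any SAP rule for telling these records apart.

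Several other replies also hold:

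- The safety endpoints are summarised descriptively, with no between-group test planned. Solicited and unsolicited AEs appear on separate lines of the SAP 8.3.2 summary with no combined total. A reader might infer that the double entry biases a formal comparison or inflates a total AE count; the documents plan neither. A count of unique subjects with any AE would not change.
- A reader might infer that the plan will misreport how long reactions last. SAP section 8 names no duration summary, and the Day 0 to 7 data remain in the diary and are to be listed. Only the duration attached to the unsolicited record is short.
- Protocol 1.6 also says that most symptoms with AS03-adjuvanted influenza vaccines were short-lived, which argues against a high carry-over rate.
- A solicited-type term starting exactly eight days after a dose can be recognised in a listing, and the error overstates unsolicited AEs and hides none. But the summary tables, which most readers use, do not show it.
- Protocol 12.1.2 refers to eCRF completion guidelines that are not among the documents. They may already link the records, so the need for a new eCRF field is not shown. The gap in the SAP remains.

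**Conclusion.** The point holds as a gap in SAP handling. Followed as written, the plan counts reactions that developed in the solicited window as unsolicited AEs in endpoint 3, without exception, and does not identify them.

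The size is unknown because no carry-over rate is given. A rise of 3-10 percentage points in the arm difference is an upper bound, resting on three assumptions: 3-10% carry-over under MT-2766, none under placebo, and no other unsolicited AEs in the affected subjects. An independent 20% background reduces it to 2.4-8 points. That the excess falls mainly on MT-2766 is a reasonable expectation from Protocol 1.6, not a documented fact for this vaccine. Entry into the most-frequent table needs 6 of 100 or 2 of 25 subjects with the same term.

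The duration error is exact (8 minus the onset day, so 1 to 8 days) but confined to listings and any ad hoc output. A reader might also infer that the unsolicited record should simply be set to related. The documents do not support that: Protocol 12.1.9 requires the investigator's assessment for each unsolicited AE, and endpoint 3 reports it.

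**What to change.** Keep the Day 8 entry, and change the SAP as follows:

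- **Flag.** Derive a continuation flag in the analysis data from the diary and AE records: a solicited-type term starting eight days after a dose, with the same reaction still present in that dose's diary on Day 7.
- **SAP 8.3.1.2 and 8.3.2.2.** Present unsolicited AEs and the most-frequent table both with and without flagged records.
- **SAP 7.1.3.1.** For flagged records, compute duration from the first diary day of the reaction to the stop date, and state how gaps in the diary are treated.
- **Causality.** Leave the investigator's assessment on the unsolicited record unchanged. In the listing, show beside it that the linked solicited record is related by rule.

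The cost is one derived flag, some SAP wording and one extra set of tables. No further data collection is needed, so the change remains possible although SAP 10 reports that the study was discontinued. If the relevant data are already locked, Protocol 14.5 requires the added analysis to be described in the study report and kept distinct from the planned results.
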